3.2.3 Objective response rate (ORR)

ORR (per RECIST 1.1 as assessed by the BICR) is defined as the number (%) of patients with at least 1 visit response of CR or PR (i.e. unconfirmed response) and will be based on a subset of all randomized patients. If the BICR finds any patients do not have measurable disease at baseline then the analysis of ORR for the BICR data will exclude these patients, so that the denominator is a subset of the randomized patients who have measurable disease at baseline per BICR for either reviewer. Therefore, data obtained up until progression, or the last assessment in the absence of progression, will be included in the assessment of ORR. Patients who discontinue randomized treatment without progression, receive a subsequent anti-cancer therapy (note that radiotherapy is not considered a subsequent anti-cancer therapy) and then respond will not be included as responders in the ORR.

ORR will also be obtained using the algorithm described above for the RECIST site investigator tumor data. The denominator for ORR will be all randomized patients with measurable disease at baseline per the site investigator.

For exploratory purposes, ORR may also be obtained for the irRECIST 1.1 data obtained from BICR.

3.2.4 Duration of response (DoR)

DoR (per RECIST 1.1 as assessed by the BICR) will be defined as the time from the date of first documented response until the first date of documented progression or death in the absence of disease progression (i.e. date of PFS event or censoring – date of first response + 1). The end of response should coincide with the date of progression or death from any cause

used for the PFS endpoint. The time of the initial response will be defined as the latest of the dates contributing towards the first visit response of CR or PR.

If a patient does not progress following a response, then their DoR will be censored at the PFS censoring time.

DoR will not be defined for those patients who do not have documented response.

3.2.5 Progression-free survival at 18 months and 24 months (PFS18 and PFS24)

The PFS18 and PFS24 will be defined as the Kaplan-Meier estimate of PFS (per RECIST 1.1 as assessed by the BICR) at 18 months and 24 months, respectively.

3.2.6 Time to death or distant metastasis (TTDM)

TTDM (per RECIST 1.1 as assessed by BICR) will be defined as the time from the date of randomization until the first date of distant metastasis or death in the absence of distant metastasis. Distant metastasis is defined as any new lesion that is outside of the radiation field according to RECIST 1.1 or proven by biopsy. For this reason, the TTDM endpoint will be determined from recurrent disease that occurs outside of the structures contained within the thorax, including lymph nodes, pulmonary, pleural, and mediastinal metastatic sites and excluding the heart. The locations of distant metastases will be defined and documented prior to database lock/unblinding.

Patients who have not developed distant metastasis or died at the time of analysis will be censored at the time of the latest date of assessment from their last RECIST 1.1 assessment. However, if the patient has distant metastasis or dies after 2 or more consecutive missed visits, the patient will be censored at the time of the latest evaluable RECIST 1.1 assessment prior to the 2 missed visits. If the patient has no evaluable visits or does not have baseline data they will be censored at Day 1 unless they die within 2 visits of baseline.

A sensitivity analysis of TTDM may be performed using Investigator assessments according to RECIST 1.1.

3.2.7 Proportion of patients alive at 24 months and 36 months after randomization (OS24 and OS36)

The OS24 and OS36 will be defined as the Kaplan-Meier estimate of OS at 24 months and 36 months after randomization, respectively.

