Durvalumab immunogenicity assessment (ADA sampling) to identify ADA responses i			X		X				8.5
Tremelimumab immunogenicity assessment (ADA sampling) to identify ADA responses j			X		X				8.5

					Time since	e last dose	of IP		
	Day (±3)			Week (	±1 week)			48 weeks and every	
Evaluation	30	8	12	16	24	32	40	8 weeks (±2 weeks) until study termination or death	For details, see Section
Whole blood for gene expression (PaxGene-RNA tubes, not applicable for China)	X	X							8.8
Circulating soluble factors (including TMB; plasma, not applicable for China)	X	X							8.8
EORTC QLQ-LC13 (by e-device) k		Weekly (±1 day on weeks 1, 2, 3, 5, 6 and 7, and ±3 days on weeks 4 and 8) for the first 8 weeks from randomization and then every 4 weeks (±3 days) relative to randomization until study termination or PFS2 or death							
EORTC QLQ-C30 (by e-device) k	Every 4	weeks (±3	3 days) rela	tive to rand	lomization	until study	termination	n or PFS2 or death	8.1.3
PRO-CTCAE (by e-device) k				hen every 4		days) rela		4, 8 and 12) for the first omization until study	8.1.3
PGIS (by e-device) k	Every 8	weeks (±3	3 days) rela	tive to rand	lomization	until study	termination	n or PFS2 or death	8.1.3
EQ-5D-5L (by e-device) k	Every 8	weeks (±3	3 days) rela	tive to rand	lomization	until study	termination	n or PFS2 or death	8.1.3
Health resource use module (HOSPAD)					X			X m	8.9
Tumor assessment (CT or MRI) (RECIST 1.1) 	On-study tumor assessments occur q8w ±1w for the first 72 weeks (relative to the date of randomization), followed by q12w ±1w until up to 96 weeks relative to the date of randomization, and then q24w ±1w thereafter (relative to the date of randomization) until RECIST 1.1-defined radiological progression, plus one follow-up scan no earlier than 4 weeks later and no later than the next regularly scheduled imaging visit. This on-study schedule MUST be followed regardless of any delays in dosing. Additional scans to be completed per standard practice post-progression. Tumor assessments up to progression may continue after the PFS analysis and up to the end of the study						8.1		

For women of childbearing potential only. A urine or serum pregnancy test is acceptable.

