#### 9.4.1.6 Time to death or distant metastasis

TTDM will be defined as the time from the date of randomization until the first date of distant metastasis or death in the absence of distant metastasis. Distant metastasis is defined as any NL that is outside of the radiation field according to RECIST 1.1 or proven by biopsy. Patients who have not developed distant metastasis or died at the time of analysis will be censored at the time of the latest date of assessment from their last evaluable RECIST 1.1 assessment. However, if the patient has distant metastasis or dies after 2 or more missed visits, the patient will be censored at the time of the latest evaluable RECIST 1.1 assessment prior to the 2 missed visits. If the patient

has no evaluable visits or does not have baseline data, he/she will be censored at Day 1 unless they die within 2 visits of baseline.

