3. PRIMARY AND SECONDARY VARIABLES

3.1 Derivation of RECIST Visit Responses

For all patients, the RECIST tumor response data will be used to determine each patient's visit response according to RECIST version 1.1 (see further Appendix F of the CSP). It will also be used to determine if and when a patient has progressed in accordance with RECIST and their best objective response to study treatment.

Baseline radiological tumor assessments are to be performed post-cCRT within the 42 days before randomization and start of study treatment. Tumor assessments are then performed every 8 weeks (\pm 1 week) for the first 72 weeks (relative to the date of randomization), followed by every 12 weeks (\pm 1 week) up to 96 weeks (relative to the date of randomization), and then every 24 weeks (\pm 1 week) thereafter (relative to the date of randomization) until RECIST 1.1-defined radiological progression, plus one follow-up scan no earlier than 4 weeks later and no later than the next regularly scheduled imaging visit.

If an unscheduled assessment is performed, and the patient has not progressed, every attempt should be made to perform the subsequent assessments at their scheduled visits. This schedule is to be followed to minimize any unintentional bias caused by some patients being assessed at a different frequency than other patients.

From the investigator's review of the imaging scans, the RECIST tumor response data will be used to determine each patient's visit response according to RECIST version 1.1. At each visit, patients will be programmatically assigned a RECIST 1.1 visit response of CR, PR, SD or Progressive disease (PD), using the information from target lesions (TLs), non-target lesions (NTLs) and new lesions and depending on the status of their disease compared with baseline and previous assessments. If a patient has no evidence of disease (NED) at baseline, then the patient will be assigned a visit response of NED if there is still no evidence of disease or PD if there is evidence of progression. If a patient has had a tumor assessment which cannot be evaluated, then the patient will be assigned a visit response of not evaluable (NE) (unless there is evidence of progression in which case the response will be assigned as PD).

RECIST outcomes (i.e. PFS and ORR etc.) will be calculated programmatically for the BICR and site investigator data from overall visit responses.

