3.1.1 Blinded Independent Central Review (BICR) assessment using RECIST 1.1

A planned BICR of all radiological imaging data will be carried out using RECIST version 1.1. All radiological scans for all patients (including those at unscheduled visits, or outside visit windows) will be collected on an ongoing basis and sent to an AstraZeneca appointed Contract Research Organization (CRO) for central analysis. The imaging scans will be reviewed by 2 independent radiologists using RECIST 1.1 and will be adjudicated, if required

(i.e. two reviewers' review the scans and adjudication is performed by a separate reviewer in case of a disagreement). For each patient, the BICR will define the overall visit response (i.e. the response obtained overall at each visit by assessing TLs, NTLs and new lesions) data and no programmatic derivation of visit response is necessary (for patients with TLs at baseline: CR, PR, SD, PD, NE; for patients with NTLs only: CR, SD, PD or NE; for patients with no disease identified at baseline: PD, no evidence of disease [NED], NE). If a patient has had a tumor assessment that cannot be evaluated, then the patient will be assigned a visit response of NE (unless there is evidence of progression in which case the response will be assigned as PD). RECIST assessments/scans contributing towards a particular visit may be performed on different dates and for the central review the date of progression for each reviewer will be provided based on the earliest of the scan dates of the component that triggered the progression.

If adjudication is performed, the reviewer that the adjudicator agreed with will be selected as a single reviewer (note in the case of more than one review period, the latest adjudicator decision will be used). In the absence of adjudication, the records for all visits for a single reviewer will be used. The reviewer selected in the absence of adjudication will be the reviewer who read the baseline scan first. The records from the single selected reviewer will be used to report all BICR RECIST information including dates of progression, visit response, censoring and changes in target lesion dimensions. Endpoints (of ORR, PFS and DoR) will be derived programmatically from this information.

Results of this independent review will not be communicated to Investigators and the management of patients will be based solely upon the results of the RECIST 1.1 assessment conducted by the Investigator.

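### The two-missed-visit rule for TTDM makes no exception for patients whose scans ended at intrathoracic progression, so many of their later deaths can be censored

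*SAP*

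**What the plan says.** **Endpoint.** SAP 3.2.6 runs TTDM from randomization "until the first date of distant metastasis or death in the absence of distant metastasis". Only "recurrent disease that occurs outside of the structures contained within the thorax" counts as distant, so an intrathoracic progression is not a TTDM event.

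**Missed visits.** In the SAP, "if the patient has distant metastasis or dies after 2 or more consecutive missed visits, the patient will be censored" at the latest evaluable RECIST assessment before the missed visits. Protocol 9.4.1.6 has the same rule: "if the patient has distant metastasis or dies after 2 or more missed visits, the patient will be censored". Appendix B of the SAP implements the rule for RECIST assessments by elapsed time. An event, including a death, counts only if an assessment lies in the two-visit window before it.

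**End of imaging.** Under SAP 3.1, scans run "until RECIST 1.1-defined radiological progression, plus one follow-up scan no earlier than 4 weeks later". Protocol 7.1.1 agrees and keeps all patients in survival follow-up until the end of the study, so later death dates are known.

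**Scans after progression.** Protocol Table 2 says only: "Additional scans to be completed per standard practice post-progression". SAP 3.1.1 says that all scans for central review, "including those at unscheduled visits, or outside visit windows) will be collected on an ongoing basis", and SAP 3.2 admits unscheduled RECIST assessments.

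**Sensitivity analysis.** SAP 4.2.7 does not repeat the PFS sensitivity analyses of 4.2.2 for TTDM, and these include the attrition-bias analysis. Only an optional analysis of investigator assessments remains.

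**The concern.** The two-missed-visit rule suits PFS, because scheduled imaging and the endpoint both end at progression. For PFS2 (SAP 3.2.8) the rule is tied to status reviews that continue every 8 weeks after progression. TTDM has neither feature. After an intrathoracic progression the patient is still at risk of a TTDM event, but the scan schedule has ended.

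A death well after the follow-up scan then looks, by elapsed time, like a death after missed visits, and it is censored back to that scan. No visit had been planned. Patients with local progression have a poor outlook, so this censoring is informative. At stake are lost events and TTDM curves that are too high on a secondary endpoint that is meant to count death.

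**Working it through.** **1. The plan's windows.** The Appendix B arithmetic reproduces:
- Within two visits of baseline: 2×56+7 = 119 days.
- q8w: (1+8+8+1)×7 = 126 days.
- q8w to q12w: (1+8+12+1)×7 = 154 days.
- q12w: (1+12+12+1)×7 = 182 days.
- q12w to q24w: (1+12+24+1)×7 = 266 days.
- q24w: (1+24+24+1)×7 = 350 days.

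**2. Post-progression survival (assumption).** The documents give no figure for intrathoracic-only progression. Median PFS is 10 months on placebo and 10/0.65 = 15.4 on durvalumab. Median OS is 24 months and 24/0.73 = 32.9. I take the differences: 24−10 = 14 months and 32.9−15.4 = 17.5 months. I also assume that no scan after the follow-up scan is read centrally.

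**3. Closed form.** With exponential survival, the share of deaths outside the window is 0.5^(gap/median). The gap is the window plus the time from progression to the follow-up scan, and a month is 30.4375 days. For a 14-month median:
- 126-day window, no follow-up scan: 126/30.4375 = 4.14 months; 0.5^(4.14/14) = 82%.
- Scan at 4 weeks: 154 days, 78%. Scan at 8 weeks: 182 days, 74%.
- 350-day window, no follow-up scan: 57%. Scan at 24 weeks: 518 days, 43%.

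**4. Simulation over all windows.** This uses the protocol scan schedule, the window that applies on the day of death, and cut-offs from 36 months (after the last randomization) to 36+38 = 74 months (after the first). Share of deaths after progression that are censored:

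| Arm (median PFS, post-progression) | No follow-up scan | Scan at 4 weeks | Scan at next visit |
|---|---|---|---|
| Placebo (10, 14 months) | 68% | 64% | 57% |
| Durvalumab (15.4, 17.5 months) | 67% | 63% | 56% |

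Over both PFS medians and all three follow-up-scan cases, the share is 45-62% for a post-progression median of 10 months, 40-57% for 8, 32-49% for 6 and 26-43% for 4.8.

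**5. Events lost.** Base case, all assumed:
- First events are 40% intrathoracic progression, 45% distant and 15% death.
- After intrathoracic progression, distant metastasis occurs at 0.08 and death at 0.03 per month. Death after metastasis occurs at 0.10 per month.
- Accrual takes 38 months.

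At month 60, events per 524 patients fall from 417 to 358: 1−358/417 = 14%. Repeat runs gave 416 to 356 and 415 to 355. Month 60 is late, however, with about 449 PFS events against the planned 370. At month 46, with about 370 PFS events, about 36 deaths are lost if the follow-up scan is at the next visit, or about 11% of TTDM events. The share of such deaths censored at that point is 52-63%, depending on the follow-up scan.

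**6. Hazard ratio.**

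| Scenario (drug effect ends at local progression) | Present rule | Deaths counted | Scanning continued |
|---|---|---|---|
| Equal effect | 0.664 | 0.674 | 0.682 |
| Distant failure only | 0.609 | 0.644 | 0.657 |
| Local failure only | 0.767 | 0.754 | 0.748 |

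In the equal-effect case the shift from the present rule to deaths counted is ln(0.674/0.664) = 0.015. The standard error is about 2/√358 = 0.106, so the shift is 0.14 standard errors. The largest shift shown is ln(0.644/0.609) = 0.056, about 0.5 standard errors. If the drug effect persists after progression, the present rule was closer to continued scanning in two of three scenarios: 0.621 (0.630 with deaths counted) against 0.619, and 0.664 (0.693) against 0.669.

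**The case against.** **The text does not say it.** A reader might infer that the SAP declares unscheduled visits to be missed. It does not. Section 3.2.6 neither defines a missed visit after progression nor cites Appendix B, and on a literal reading a visit that was never due cannot be missed. This stands as a point about wording. But Appendix B is headed for RECIST 1.1 assessments in general, it has no exception for an ended schedule, and the SAP amendment history lists 3.2.6 and Appendix B together for this rule. The look-back is therefore the likely implementation, and two programmers could still build different datasets.

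**Later scans may be read.** Any centrally read scan inside the window keeps a later death as an event, so the shares above are upper-range figures. Against that, no schedule exists for such scans. After treatment is stopped for progression, a Table 2 footnote provides for collecting local CT/MRI readings from charts. How far BICR reads is left to a charter that is not among these documents.

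**Counting deaths has its own bias.** This stands. Under the base-case rates, 0.08/(0.08+0.03) = 73% of patients metastasise before dying. About 75-80% of the censored deaths follow an unobserved metastasis, on average about 8 months earlier in the month-60 run. Counting the death dates the event that much late. Patients alive after local progression remain censored at their last scan, so time after that scan would count only for those who die.

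**The consequence is limited.** TTDM is outside the multiple testing procedure, has no event target or power, and OS captures every death. This also stands.

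**Conclusion.** The gap is real. The documents count death as a TTDM event, do not count intrathoracic progression, stop scheduled scans there, and give the missed-visit rule no exception for it. Under the look-back, known deaths that meet the endpoint definition are censored.

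The size rests on two assumptions that the documents do not settle: post-progression survival, and no centrally read scans after the follow-up scan. With both, roughly half to two thirds of these deaths are lost under the planning medians, and 26-62% if the post-progression median is 4.8-10 months. Base-case TTDM events fall by about 11% at about 370 PFS events and 14% at month 60. TTDM curves are generally too high.

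Two stronger readings are tempting. One is that most such deaths are lost whatever the assumptions; the low end of the range rules that out. The other is that counting deaths always gives the better hazard ratio and should replace the present rule. The scenarios with a persisting drug effect contradict the first part, and neither version is free of informative censoring. The hazard ratio shift is small and its direction depends on the scenario. The dual primary endpoints are not affected.

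**What to change.** In SAP 3.2.6:

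1. State that visits after RECIST progression plus the one follow-up scan are not missed visits for TTDM.
2. State whether scans taken after progression are read by BICR for TTDM.
3. Pre-specify and report TTDM two ways: with every death without documented distant metastasis after such a progression counted on the date of death, and under the present censoring rule. Amend 4.2.7, which now rules out any such sensitivity analysis.
4. Name the limits of counting deaths. An unobserved earlier metastasis is dated at death, possibly several months late, and patients alive after local progression stay censored at their last scan.

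List the departure from protocol 9.4.1.6 in SAP section 6. The cost is a few sentences, a small programming change and one more analysis. No extra patient data are needed, because survival is already followed. The change should be settled before the database lock, when the SAP already requires the distant sites to be documented.

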3.2.8 Time from randomization to second progression or death (PFS2)

PFS2 will be defined as the time from the date of randomization to the earliest of the progression event subsequent to the first subsequent anticancer therapy (excluding radiotherapy) or death (i.e. date of PFS2 event or censoring – date of randomization + 1). The date of second progression will be recorded by the investigator in the eCRF at each assessment and defined according to local standard clinical practice and may involve any of

the following: objective radiological imaging, symptomatic progression or death. The date of the PFS2 assessment and investigator opinion of progression status (progressed or non-progressed) at each assessment will be recorded in the eCRF. Patients must have had a first progression event and received subsequent systemic anticancer therapy (excluding radiotherapy) for a second progression event to be valid. Second progression status will be reviewed every 8 weeks following the progression event used for the primary variable PFS (the first progression) and status recorded. Patients alive and for whom a second disease progression has not been observed should be censored at the earliest of: date of study termination, date last known alive, DCO, or if a patient has not had a first subsequent therapy; the date last known not to have received a first subsequent therapy (TFST censoring date).

However, if the patient experiences a second progression or dies after 2 or more consecutive missed visits, the patient will be censored at the time of the last PFS2 assessment prior to the 2 missed visits.

